3) Recruits may be concerned about the exposure to radiation from a CT scan. The amount of radiation delivered by one low dose CT scan of the chest to a standard-sized adult is approximately 1 mSv (in clinical practice a routine chest CT examination may be up to 10 mSv). 1 mSv is approximately equivalent to 5 months' worth of natural background radiation. The International Committee on Radiological Protection advises that there may be a small chance that low amounts of radiation may cause cell damage that will manifest itself as cancer many years after the exposure. In the UKLS protocol the radiation dose will almost invariably be less than 1 mSv. According to the Twelfth COMARE deliberations there is no threshold below which there is no deleterious effect from radiation. The risk of cancer induction for one low dose CT scan (UKLS protocol) is estimated at 1 in 20,000 for a healthy 50-year-old (this is additional to the lifetime likelihood of developing cancer of approximately 1 in 4). We will make the above information clear to all potential participants during the consent process.

4) Diagnostic workup may cause anxiety in recruits: Diagnostic work-up of patients with suspicious nodules may include bronchoscopies, biopsies, staging CT with contrast, PET scan, and surgical resection. The great majority of suspicious nodules will not grow and will be regarded as benign. This will be made clear to subjects recalled for additional investigation. The detection of such nodules is an unavoidable part of the screening programme. The Participant Information Booklet will provide a detailed explanation of why follow-up CT is needed in a relatively high proportion of subjects and associated risks. Modelling based on preliminary results from other screening trials has indicated that clinical work-up will only occur in a very small proportion of the CT screened population (estimated at 1.5% of which 70% will have lung cancer). The proportion of subjects that undergo these tests is kept low by application of the UKLS care pathway that ensures subjects are filtered by less invasive tests (repeat CT) until the probability of malignancy is sufficiently high to warrant invasive tests or resection. This requires strict adherence to the CT screening protocol and the rigorous training of the radiologists and radiographers.

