15.2 Sample Size

The sample size/power calculations had the aim of determining a screening schedule which would optimise when and with what study size a significant result is likely in UKLS, with respect to the comparison of lung cancer mortality in the intervention and control group. The question of particular interest is whether a study offering only a single screen to the study group, or one offering multiple screens, is likely to be more efficacious in terms of:

- (1) how soon a significant result can be expected; and
- (2) resources expended on screening

Without actually carrying out the full trial, the timing and magnitude of the effect on mortality, if any, cannot be known for certain. We can, however, arrive at estimates using published data on the following quantities:

- The incidence of lung cancer in the target population
- Uptake of screening
- The mean sojourn time (MST) of asymptomatic lung cancer (i.e. the duration of the window of opportunity for asymptomatic detection) and its inverse, the rate of progression from asymptomatic to symptomatic disease
- Sensitivity of the screening test, CT scanning
- Survival of asymptomatic lung cancer cases, possibly taking into account length bias/over diagnosis

- Survival of symptomatic lung cancer cases

Single screen design

Although we shall use estimates of instantaneous rates of transition (e.g. from asymptomatic to symptomatic disease, from alive to dead), we shall convert these to discrete time probabilities, to obtain simple deterministic models. Let:

I = Annual incidence rate of lung cancer in target population

λ_1 = Instantaneous rate of transition from asymptomatic to symptomatic disease (=1/MST)

λ_2 = Instantaneous death rate from lung cancer of asymptomatic cases

λ_3 = Instantaneous death rate from lung cancer of symptomatic cases

S = sensitivity of the screening test

We assume a uniform annual incidence and exponential rates of progression to symptomatic disease and death [25]. We first demonstrate how to estimate the cumulative death rates in intervention and control groups for the simple case of a single screen study. In the intervention group, at time point 0, the expected rate of detection of asymptomatic lung cancers in those attending for screening is:

$$P = \frac{IS}{\lambda_1}$$

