We now require estimates of the various quantities. Let us first suppose that we shall be selecting a fairly high risk group for the trial, with a minimum annual incidence of five per thousand and an average annual incidence of seven per thousand. Thus $I=0.007$. From a recently published overview, we have estimates $\lambda_1=0.49$ and $S=0.96$ [28]. Five-year survival from lung cancer in the UK has been reported as 6% [29], corresponding to $\lambda_3=0.56$. Henschke et al [30] report 85% 10-year survival of 412 stage I screen-detected cases. Assuming that the 72 screen-detected cases in their series with stage II or worse disease had zero ten-year survival, this would give an overall ten-year survival of 72%. Hypothesising further that this is artificially high as a result of length bias/overdiagnosis, we assume a ten-year survival of 50%. Thus we are estimating the effect of screening on mortality from the 'real', life-threatening tumours, rather than inflating the incidence of the intervention group and retaining the very high survival rate. This gives $\lambda_2=0.07$. We assume an uptake rate of 80%, which seems high but reflects the motivated nature of this group, already demonstrated by their positive response at two stages of approach.

WALD Single Screen Design

The resulting estimates of cumulative lung cancer mortality are shown in Table 1, adjusted for the 80% compliance. The Table also shows the relative risks of lung cancer death, and the numbers required per group (assuming equal group size) for 90% power to detect the difference as significant, with 2-sided testing at 5% level. The optimum time of analysis would be at the end of three years, and 16,000 subjects per group would be required (32,000 in all). The time to the result, taking into account the recruitment period, would be more likely to be around five years.

Year	Cumulative lung cancer mortality (study)	Cumulative lung cancer mortality (control)	RR (intervention vs control)	Number required per group
1	1.0	1.2	0.83	368,000
2	3.1	4.0	0.78	63,000
3	5.3	7.8	0.69	16,000
4	9.2	12.1	0.76	20,000
5	13.4	16.7	0.80	21,000
6	17.9	21.4	0.83	24,000

Annual screening for three years

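### The incidence stated in section 15.2 implies a 1.37% cancer yield at the scan, against 1.05% in section 4.4.1; Table 1 was evidently run at a lower incidence, and its rates give about 79% power at 16,000 per group, not 90%

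*Protocol*

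**What the plan says.** Section 4.4.1, item 4, describes the burden of diagnostic work-up. From modelling on preliminary results of other screening trials, it expects clinical work-up in a very small proportion of those who are CT-screened, "estimated at 1.5% of which 70% will have lung cancer".

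Section 15.2 gives a formula, P = IS/λ1, and says that "the expected rate of detection of asymptomatic lung cancers in those attending for screening is" this quantity. It then fixes the inputs. The target group is to have a "minimum annual incidence of five per thousand and an average annual incidence of seven per thousand", and the text takes I = 0.007 from the second figure. S = 0.96 and λ1 = 0.49 come from a published overview. The section also sets λ2 = 0.07, λ3 = 0.56 and uptake at 80%.

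Table 1 gives cumulative lung cancer mortality and the number needed per group for "90% power to detect the difference as significant, with 2-sided testing at 5% level", "assuming equal group size". The year-3 row reads "5.3 7.8 0.69 16,000" (study and control deaths per 1000, relative risk, number per group), and the design of 16,000 per group rests on that row.

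**The concern.** Both figures describe the same thing: the share of people scanned whose cancer is found because of the scan. The protocol never prints P, so a reader does not see that the two sections differ.

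The benefit modelled in 15.2 comes only from cancers detected at the single screen, so the assumed yield drives the mortality difference and hence the sample size. The 4.4.1 figures describe possible harm to participants. If the 15.2 inputs are right, the expected work-up rate is too low. If the 4.4.1 yield is right, at least one stated input in 15.2 is wrong. The pilot will also observe a detection rate, and the protocol offers two different values to compare it with.

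**Working it through.** **1. The two yields.**
- Section 15.2: P = IS/λ1 = 0.007 × 0.96 / 0.49 = 0.01371, or 1.37% of attenders.
- Section 4.4.1: 0.015 × 0.70 = 0.0105, or 1.05%.
- Rounding: 1.45% × 65% = 0.94% and 1.55% × 75% = 1.16%, so 1.37% is out of reach.
- To find 1.37% with 1.5% worked up, 1.37/1.5 = 91% of work-ups would have to be cancer. At 70%, 1.37/0.70 = 1.96% would have to be worked up.

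**2. Which incidence is behind Table 1?** The control-group formula is D0 = I Σ(1 − exp(−λ3(i − 0.5))), i = 1 to r, with λ3 = 0.56. At year 3 the sum is 0.2442 + 0.5683 + 0.7534 = 1.566. Deaths per 1000:

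| Year | Table 1 control | I = 0.005 | I = 0.007 |
|---|---|---|---|
| 1 | 1.2 | 1.22 | 1.71 |
| 2 | 4.0 | 4.06 | 5.69 |
| 3 | 7.8 | 7.83 | 10.96 |
| 4 | 12.1 | 12.13 | 16.98 |
| 5 | 16.7 | 16.72 | 23.41 |
| 6 | 21.4 | 21.49 | 30.09 |

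The printed column agrees with I = 0.005 to within 0.1 in every year and with I = 0.007 in none. The yield that goes with I = 0.005 is 0.005 × 0.96 / 0.49 = 0.98%.

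**3. The stated 90%.** For two proportions, two-sided 5%, pooled variance, year 3: p1 = 0.0053, p0 = 0.0078, mean 0.00655. At 16,000 per group the standard error is √(2 × 0.00655 × 0.99345 / 16,000) = 0.000902. The standardised difference is 0.0025/0.000902 = 2.77, and 2.77 − 1.96 = 0.81, which is a power of 79% (76–82% allowing for rounding in the table). The numbers needed are 21,878 per group for 90% and 16,343 for 80%. The other later rows behave the same way: 80% power needs 19,666, 21,367 and 24,685 in years 4 to 6, against printed values of 20,000, 21,000 and 24,000. The stated 90% does not reproduce, before any change in yield.

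**4. Power of 16,000 per group at a yield of 1.05%.**
- *Through incidence.* I = 0.0105 × 0.49 / 0.96 = 0.00536. The 15.2 formulas were run with 80% uptake. The cumulative symptomatic cancers after the screen were taken as rI(1 − PS), because the printed expression lacks the factor r, and alternatively as the direct exponential form. Year 3: 6.05–6.10 vs 8.39 per 1000, power 68–70%. Year 4: 9.82–9.88 vs 13.00, power 75–76%.
- *From Table 1.* Relative to the 0.98% behind it, 1.05% is a factor of 1.07. Scaling both year-3 rates gives 5.68 vs 8.36 per 1000 and 82%. Scaling only the benefit gives 5.12 vs 7.8 and 85%.
- The two routes differ partly because the printed year-3 study value of 5.3 is lower than the formulas give at I = 0.005 (5.6–5.7).
- *Through another parameter.* Keeping I = 0.007 and lowering the yield through λ1 (to 0.64) gives 75–79% over years 3–4; through S (to 0.735) it gives 55–73%. The documents do not say which would apply.

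No route reaches 90%.

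**The case against.** **The figures have different sources and purposes.** The 1.05% is a rounded expectation from other trials, placed in a paragraph about anxiety, and 15.2 says that its modelling was repeated with other parameters. This stands as far as it goes: a factor of 1.3 between two external estimates is modest. But λ1 and S are external too, 4.4.1 presents its figure as what the trial's own care pathway will produce, and neither section mentions the other.

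**The denominator may be everyone allocated to CT.** Then 1.37% × 80% = 1.10%, inside the rounding range, and the conflict nearly vanishes. The wording of 4.4.1 refers to people who are screened, and non-attenders are not.

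**Table 1 does not need 1.37%.** This is the strongest objection, and it stands. The rates behind 16,000 carry a yield of 0.98%, which 1.05% slightly exceeds. It moves the fault into 15.2, where the text states one incidence and the table uses another; it does not remove it.

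**A stronger reading that should be resisted.** A reader might infer that the lower yield takes power from 90% down to 70–81%. That range comes from shrinking the nominal 3.24 by the yield ratio 0.766: 3.24 × √0.766 − 1.96 = 0.88 (81%), or 3.24 × 0.766 − 1.96 = 0.52 (70%). It starts from a 90% that Table 1 does not support and assumes that Table 1 was run at 1.37%. Neither holds, so the range should not be used.

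**Conclusion.** Section 15.2 as worded and section 4.4.1 give incompatible yields. The simplest explanation is that the incidence printed in the text, 0.007, is not the one used for Table 1. At 0.005 and 70% positive work-ups, 0.98/0.70 = 1.4% would be worked up, close to the 1.5% stated. It therefore does not follow that the work-up estimate is wrong: about 2.0% would be expected only if 0.007 is the true design incidence, which would mean about 251 rather than 192 of the 12,800 planned scans (12,800 × 1.96% and × 1.5%).

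Separately, 90% power at 16,000 per group is not supported, and the yield is not the sole cause, since Table 1 as printed already falls short. The power at 1.05% depends on whether the formulas or the printed table are followed.

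The two yields and the fit of the control column follow from printed figures. The power values assume a comparison of cumulative proportions without continuity correction. That 0.005 was the value actually used is an inference from the fit.

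**What to change.** Decide on one design incidence and use it throughout section 15.2. Print the implied yield P beside the inputs and use the same yield in section 4.4.1, item 4, so that the pilot's detection rate has one comparator. Re-run Table 1 from those inputs, including the year-3 study rate, and replace the 90% statement with the power that 16,000 per group then gives.

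If the design incidence is 0.005, the 1.5% and 70% can stay, with a note that they are consistent with P to rounding. Only if 0.007 is confirmed should the work-up estimate rise to about 2.0%, in any participant-facing text as well.

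The cost is one re-run of the model, wording changes in two sections, and a less favourable stated power. No extra participants are needed to correct the statement. Keeping 90% as the target would be a separate decision, at about 21,900 rather than 16,000 per group on Table 1's present rates.

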4.4.2 Known Potential Benefits

There are no completed and reported randomised controlled trials (RCT) in lung cancer screening available to assess the benefits of lung cancer screening compared to no intervention at all. However, evidence from preliminary data from a wide range of international observational studies indicates that the technology is clearly effective in detecting disease before patients develop symptomatic lung

cancer [20]. Surgical resection at an early stage of the disease remains the only realistic option for a cure. Thus the obvious next stage of research is a randomised trial to estimate the effect of the screening on mortality from lung cancer.

5 Selection of Centres/Clinicians

Each participating Centre (and investigator) has been identified on the basis of:

- National Thoracic Centre in an NHS setting with large case load of lung cancer patients
- Lead clinicians in Radiology, Respiratory Medicine, Pathology and Surgery with a specific interest in the management of early lung cancer
- Population with a high risk of developing lung cancer within the vicinity of the Centre
- Support from the Trust's CEO. All the Clinical leads indicating an enthusiasm to participate in the study
- Ensuring that sufficient time, staff and adequate facilities are available for the trial
- Providing information to all supporting staff members involved with the trial or with other elements of the patient's management
- Discussion and agreement to UKLS trial costings
- Agreement to utilise the UKLS Protocols and Care Pathway
- Acknowledging and agreeing to conform to the administrative and ethical requirements and responsibilities of the study, including signing-up to Good Clinical Practice (GCP) and other regulatory documentation
- Centre fitting demographic considerations for undertaking a lung cancer screening trial

5.1 Centre/Clinician Inclusion Criteria

- a. Positive Site Specific Assessment (SSA) by local Research and Development (R&D) department
- b. Signed Research Site Agreement (RSA)
- c. Receipt of evidence of completion of (a) & (b) by LCTU
- d. Completion and return of 'Signature and Delegation Log' to LCTU
- e. Curriculum Vitae (CV) including a record of International Conference for Harmonisation (ICH) of GCP training – Principal Investigator (PI)
- f. CV including a record of ICH GCP training – Other personnel on the delegation log
- g. Signed Clinical Study Protocol Receipt Form
- h. Provision of Patient Information Sheet, Consent Form and other required documentation on trust headed paper
- i. ARSAC Approval for performing the CT scans

5.2 Centre/Clinician Exclusion Criteria

Those centres that do not fulfil the above inclusion criteria will not be permitted to participate in the trial.

6 Trial design – Main UKLS Trial

6.1 Primary Endpoint(s)

- To establish the impact of pre-clinical detection of lung cancer lung cancer mortality by comparing lung cancer mortality between the control group and the screened groups combined
- To establish if there is a lung cancer mortality benefit from CT screening
- Establish total mortality benefit
- Cost effectiveness of a national lung cancer screening programme

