4.2 Rationale

The objective of the UKLS trial is to assess whether LDCT screening and treatment of early lesions will decrease lung cancer mortality compared to a control group without screening. Additionally, a UK trial would aim to test the intervention against the criteria outlined by the UK Screening Committee, especially those concerning cost effectiveness. A useful aid to cost-effectiveness is the ability to select a population at sufficiently high risk to give a substantial harvest of tumours in return for the screening activity. The group selected should also be of sufficiently high risk that the benefits of the screening will outweigh the likely harms.

The most efficient way of controlling cost will be to screen only those individuals who are at high risk of developing the disease. There has been increasing interest in developing methods for individual risk prediction for lung cancer. Models have been developed for use within high risk groups [15], and for the general population [16], based mainly on age and smoking. The predictive accuracy of lung cancer risk models may be further improved by the addition of other epidemiological risk factors [17]. The Liverpool Lung Project (LLP) [18] has recently developed a method to calculate absolute risk of lung cancer over a defined period, based on age, sex,

smoking duration, family history of lung cancer, history of non-pulmonary malignant tumour, history of pneumonia and occupational exposure to asbestos [19]. The LLP risk questionnaire has been validated in the Harvard case control, then EUELC case control and the LLP cohort studies. The LLP risk model has distinctive strengths. Firstly, the predictor variables are all explicitly defined and can be readily assessed at the time of patient presentation and secondly, patients can be assigned to their appropriate risk class on the basis of information from the initial history alone.

The screening process confers potential harms as well as potential benefits. In a randomised trial and in any future national screening service, the screening would be provided only to those whose risk was sufficiently high that the likely benefits outweigh the likely harms.

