5) Overdiagnosis: This is a major issue of any screening trial and can only be assessed in the Main UKLS Trial. The main outcome measure of overall, all-cause mortality will not be influenced by this bias. The pilot will have insufficient power to detect differences in mortality as a result of screening and therefore this bias will only be compensated for in the main trial.

6) Treatments: A significant increase in lung cancer diagnosis and treatment through screening inevitably leads to treatment complications and costs. Lung cancer resection carries a significant complication and mortality rate, influenced by a range of patient characteristics and co-morbidities. A feature of lung cancer surgical treatments is their ongoing capacity to compromise quality of life. Accordingly, the pilot will provide an opportunity to develop and test clinical monitoring forms for all treatments provided to patients with screen-detected cancers – and to examine the associated organisational and training issues.

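### The protocol contradicts itself on the main outcome: section 6.1 ranks total mortality level with lung cancer mortality (listed twice) and section 4.4.1 calls all-cause mortality the main outcome, but the trial is sized and analysed for lung cancer mortality alone

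*Protocol*

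**What the plan says.** Protocol section 6.1, repeated under the main-study primary objectives in the Protocol Summary (section 3), lists four primary items with no order among them:

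1. a disease-specific contrast, described as "comparing lung cancer mortality between the control group and the screened groups combined";
2. a second item on the same outcome, asking whether CT reduces deaths from the disease;
3. deaths from any cause, worded as "Establish total mortality benefit";
4. an economic item, on whether a national programme would be cost-effective.

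Section 4.4.1 item 5, on overdiagnosis, says: "The main outcome measure of overall, all-cause mortality will not be influenced by this bias".

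Other sections take lung cancer mortality as the outcome. Section 4.1 names it as the endpoint of the trial evidence that is needed. Section 4.2 sets the objective, to "assess whether LDCT screening and treatment of early lesions will decrease lung cancer mortality compared to a control group without screening". Section 15.2 sizes the trial "with respect to the comparison of lung cancer mortality in the intervention and control group", and gives its group sizes for "90% power to detect the difference as significant, with 2-sided testing at 5% level". Section 15.5 anticipates a Poisson regression on cumulative lung cancer mortality, with a further analysis of the lung cancer mortality hazard over time. Sections 6.3, 8.3 and 9.1 randomise 1:1 to one CT arm or one control arm.

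**The concern.** A protocol should let a reader say before the data exist which result decides the trial. Here section 4.4.1 points to all-cause mortality, section 6.1 gives it equal rank with lung cancer mortality, and the sizing and analysis sections point to lung cancer mortality alone.

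The two outcomes are far apart in power. All-cause deaths include all the deaths that screening cannot affect, so the same absolute benefit is tested against much more noise. A significant lung cancer result beside a non-significant total mortality result is therefore likely even if screening works as assumed. On the present text one reader could call that a success under section 15.2 and another a failure under section 4.4.1.

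The first primary item adds a smaller problem: it pools several screened groups, and the design has only one.

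**Working it through.** **Inputs.** Table 1 (section 15.2), year 3: cumulative lung cancer mortality 5.3 (study) and 7.8 (control) per 1,000, a difference of 2.5; 16,000 per group; two-sided 5%; 90% power. The 80% uptake is already in these rates. The protocol gives no all-cause mortality, so 30, 45 and 60 per 1,000 over three years are assumed for the control arm, with no effect of screening on other causes.

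**The plan's own figure.** The two-proportion formula with 7.8 and 5.3 per 1,000, two-sided 5% and 90% power gives 21,878 per group, so 16,000 is not reproduced. At 80% power it gives 16,343. At 16,000 per group the standard error of the difference is about 0.902 per 1,000, so power = Φ(2.5/0.902 − 1.96) = Φ(0.81) = 79%. That shortfall is a separate point. It is used here only to keep the inputs matched.

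**A second difference, 3.5 per 1,000.** With the stated I = 0.007 and λ3 = 0.56, the control formula gives 0.007 × [(1 − e^−0.28) + (1 − e^−0.84) + (1 − e^−1.40)] = 0.007 × 1.566 = 11.0 per 1,000, not 7.8. The printed 7.8 fits I = 0.005. Scaling the difference by 7/5 gives 2.5 × 1.4 = 3.5 per 1,000 (11.0 versus 7.5). Lung cancer power at 16,000 per group is then about 90%.

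**Power for total mortality.** Power ≈ Φ(difference/SE − 1.96), with SE = √[p1(1 − p1)/16,000 + p2(1 − p2)/16,000]. For control 30 and CT 27.5 per 1,000: SE = 1.868 per 1,000, 2.5/1.868 = 1.34, power = Φ(−0.62) = 27%.

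**Split result.** This is the probability that lung cancer mortality is significant in favour of screening and total mortality is not significant. It uses a bivariate normal with each test centred at its own difference/SE and correlation √(lung cancer deaths/all deaths) in the control arm, for example √(7.8/30) = 0.51.

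| Difference per 1,000 | Lung cancer power | Control all-cause per 1,000 | Total mortality power | Split result |
|---|---|---|---|---|
| 2.5 | 79% | 30 | 27% | 54% |
| 2.5 | 79% | 45 | 19% | 61% |
| 2.5 | 79% | 60 | 16% | 65% |
| 3.5 | 90% | 30 | 47% | 44% |
| 3.5 | 90% | 45 | 34% | 57.5% |
| 3.5 | 90% | 60 | 27% | 65% |

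If lung cancer made up as much as half of all control deaths (7.8/0.5 = 15.6 per 1,000), total mortality power at a difference of 2.5 would still be only 47%.

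**False-positive rate if either mortality endpoint sufficed.** The two lung cancer items are one comparison and cost-effectiveness has no stated test, so at most two tests are involved. Independent tests would give 1 − 0.95² = 9.75%. With the correlation above, 1 − P(both |Z| < 1.96) is 9.5%, 9.1% and 8.3% when lung cancer is 10%, 25% and 50% of all deaths. These shares are assumptions.

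**The case against.** The best defence is that the operative text is consistent. The objective, the sizing, the anticipated main analysis, its supplementary hazard analysis and the deaths reported to the monitoring committee (section 18.4.7) all concern lung cancer mortality. Section 12 also refers to a disease-specific mortality endpoint. Against them stands one sentence in a risk section, with no sample size, alpha or analysis attached. A reader might infer that the deciding comparison is wholly open. The documents do not support that: their weight favours lung cancer mortality. This limits the seriousness of the point but does not remove it, because section 6.1 still ranks total mortality equally and section 4.4.1 still puts it first.

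A reader might also infer that the 5% level fails because there are four primaries. That is not supported either. The level is stated for the lung cancer comparison alone, and a longer list does not alter that test's error rate. No section claims 5% across the list, and none says that any one item is enough. Inflation to about 8% to 9.5% needs an either-suffices rule, which the protocol neither states nor excludes.

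Finally, ranking and multiplicity rules may sit in the analysis plan, which section 15.5 says is in development and which is not at hand. Their absence alone would be no finding. What stands is what the protocol itself states inconsistently: the main outcome, the duplicate item and the pooled screened groups.

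Demoting cost-effectiveness would correct no error. It has no significance test, and sections 4.1 and 4.2 make it central to the screening decision.

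**Conclusion.** Wrong as written, and to be corrected. It is not a critical fault, because neither the sizing nor the anticipated analysis changes once the wording is reconciled.

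The contradiction rests on the text alone and needs no assumption. Its size does: with 16,000 per arm and year-3 analysis, power for total mortality is about 16% to 27% on the printed difference, or 27% to 47% on the rescaled one, and a split result occurs in roughly 44% to 65% of trials. These ranges depend on the assumed control all-cause rate of 30 to 60 per 1,000 and on screening leaving other causes unchanged. The 90% power in section 15.2 cannot be read across to total mortality.

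**What to change.** - In section 6.1 and the summary, name one deciding comparison: lung cancer mortality in the CT arm versus the control arm, by randomised allocation, tested two-sided at 5%.
- Delete the duplicate lung cancer item and the reference to combined screened groups.
- Test total mortality only if that comparison is significant (fixed sequence), and report it in any case as a rate ratio with a 95% confidence interval.
- Reword section 4.4.1 item 5 so that it no longer calls all-cause mortality the main outcome. It can still be cited there as a supporting check.
- Leave cost-effectiveness as a main objective if wished, stated as having no significance test.

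The change is to wording only, with no extra participants or data. The price is that total mortality loses its co-equal standing. Keeping both mortality endpoints as sufficient at 2.5% each would cost more: on Table 1's rates, lung cancer power at 16,000 per group would fall from 79% to 70%, and 90% power would need 25,842 per group. A fixed sequence holds the 5% level with no change in sample size.
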